1.0 Objectives

1.1 Study Objectives

Describe the purpose, specific aims or objectives. State the hypotheses to be tested. Describe the treatment that is considered standard of care (i.e., indicate how patients would be treated in a non-investigational setting). Indicate if the study test article(s) is available to patients without taking part in the study.

Epidemiologic data demonstrate a clear association between endometriosis, reproductive risk factors, inflammation and cardiovascular (CV) risk ^{5,8-11}. Circulating factors, Low-density lipoprotein (LDL) and oxidized LDL (oxLDL), are two of many biomarkers of cardiovascular and inflammatory disease of endometriosis ^{9,10}. An important signaling mechanism through which circulating LDL and oxLDL act is the lectin-like oxidized LDL receptor (LOX-1). LOX-1 signal transduction functionally results in pronounced endothelial dysfunction, a hallmark of CV. We hypothesis that one factor mediating the elevated risk of cardiovascular disease in endometriosis is microRNA (miRNA) activation of LOX-1 receptor mechanisms.

Specific Aim 1. To test the hypothesis that LOX-1 receptor activation is increased leading to endothelial dysfunction in endometriosis.

Hypothesis 1A. In women with endometriosis, LOX-1 receptor activation is increased resulting in endothelial dysfunction mediated through oxidant stress, endothelial NO-synthase uncoupling, and disruptions of intracellular trafficking.

Specific Aim 2. To test the hypothesis that decreased microRNAs (i.e. let7-a, let7-b, let7-g, MiR98, Mi590-p) are driving increased LOX-1 receptor expression and function in endometriosis.

In women with endometriosis:

Hypothesis 2A. MicroRNAs will be negatively related to LOX-1 receptor expression;

Hypothesis 2B. MicroRNAs will be negatively related to endothelial function.

1.2 Primary Study Endpoints

State the primary endpoints to be measured in the study. Clinical trials typically have a primary objective or endpoint. Additional objectives and endpoints are secondary. The endpoints (or outcomes), determined for each study subject, are the quantitative measurements required by the objectives.

Measuring the selected endpoints is the goal of a trial (examples: response rate and survival).

Skin blood flow (cutaneous vascular conductance)

1.3 Secondary Study Endpoints

State the secondary endpoints to be measured in the study.

LOX-1 receptor activation (soluble LOX receptor), microRNAs (i.e. let7-a, let7-b, let7-g, MiR98, Mi590-p), OxLDL, LDL, blood pressure, heart rate

2.0 Background

2.1 Scientific Background and Gaps

Describe the scientific background and gaps in current knowledge.

Endometriosis is an estrogen-dependent gynecological disorder associated with considerable chronic pelvic pain, pain during intercourse, and is a major cause of infertility ^{1,2}. This disorder affects 6% - 10% of reproductive age women and can be as high as 35-50% in women experiencing pain or infertility ³⁻⁶. Endometriosis derives from the presence of endometrium-like tissue in sites outside the uterine cavity. While endometriosis is a local inflammatory syndrome, the inflammatory process is systemic ⁷.

Endometriosis is associated with higher risk of hypercholesterolemia and hypertension ⁸. Epidemiologic data demonstrate a clear association between endometriosis, reproductive risk factors, inflammation and cardiovascular (CV) risk ^{5,8-11}.

Endometriosis and Endothelial Dysfunction: Circulating factors including LDL and oxidized LDL are two of many biomarkers of cardiovascular and inflammatory disease of endometriosis^{9,10}. An important signaling mechanism through which circulating LDL and oxLDL act is the lectin-like oxidized LDL receptor (LOX-1). LOX-1 is a ubiquitously expressed scavenger receptor, stimulated by oxLDL, Ang II, and other inflammatory cytokines, and inhibited by estrogen¹². LOX-1 is the upstream signaling initiator of mechanisms including increased oxidant production, reduced nitric oxide (NO) metabolism, and impaired intracellular trafficking¹³. Thus, LOX-1 signal transduction functionally results in pronounced endothelial dysfunction.

2.2 Previous Data

Describe any relevant preliminary data.

Cell culture and rodent data implicate miRNAs from the let7 family in regulating LOX-1 expression and activation, and these LOX-1-specific miRNAs are similarly dysregulated in endometriosis. We propose to interrogate a direct association between endometriosis-specific miRNAs and elevated LOX-1-mediated endothelial dysfunction.

2.3 Study Rationale

Provide the scientific rationale for the research.

Cardiovascular disease (CVD) is the leading cause of death in women. Endometriosis is associated with higher risk of hypercholesterolemia and hypertension⁸. Epidemiologic data demonstrate a clear association between endometriosis, reproductive risk factors, inflammation and cardiovascular (CV) risk^{5,8-11}. Our scientific premise is that in women with endometriosis, elevated cardiovascular disease risk is the result of endothelial dysfunction and chronic systemic inflammation through LOX-1 receptor activation. We will explore microRNA (miRNA) activation of LOX-1 receptor mechanisms as one factor mediating the elevated risk of CVD in endometriosis.

Lipitor is a commonly used statin that has pleotropic effects. One of those is to inhibit the LOX receptor and decrease the microRNAs that stimulate the LOX receptor. We will test this on an acute (receptor activation level) with microdialysis and on a systemic level. Additionally, statins have been proposed and tested in animals to decrease the endometriosis associated inflammatory and microRNAs we hypothesize to be driving the accelerated CVD risk. The short term oral statin will help us delineate this putative effect/mechanism."

The current application comprises pilot experiments designed to yield data for the development of the final protocol. Modifications (e.g. doses of some of the investigational substances, number of subjects needed to complete study, etc.) to this protocol will be made in the future based on the results of the pilot experiments.

3.0 Inclusion and Exclusion Criteria

Create a numbered list below in sections 3.1 and 3.2 of criteria subjects must meet to be eligible for study enrollment (e.g., age, gender, diagnosis, etc.). Indicate specifically whether you will include any of the following vulnerable populations: (You may not include members of these populations as subjects in your research unless you indicate this in your inclusion criteria.) Review the corresponding checklists to ensure that you have provided the necessary information.

- **Adults unable to consent**
 - Review "CHECKLIST: Cognitively Impaired Adults (HRP-417)" to ensure that you have provided sufficient information. HRP-417 can be accessed by clicking the Library link in CATS IRB (<http://irb.psu.edu>).
- **Individuals who are not yet adults (infants, children, teenagers)**
 - If the research involves persons who have not attained the legal age for consent to treatments or procedures involved in the research ("children"), review the "CHECKLIST: Children (HRP-416)" to ensure that you have provided sufficient information. HRP-416 can be accessed by clicking the Library link in CATS IRB (<http://irb.psu.edu>).
- **Pregnant women**
 - Review "CHECKLIST: Pregnant Women (HRP-412)" to ensure that you have provided sufficient information. HRP-412 can be accessed by clicking the Library link in CATS IRB (<http://irb.psu.edu>).

- **Prisoners**
 - Review "CHECKLIST: Prisoners (HRP-415)" to ensure that you have provided sufficient information. HRP-415 can be accessed by clicking the Library link in CATS IRB (<http://irb.psu.edu>).
- **Neonates of uncertain viability or non-viable neonates**
 - Review "CHECKLIST: Neonates (HRP-413)" or "CHECKLIST: Neonates of Uncertain Viability (HRP-414)" to ensure that you have provided sufficient information. HRP-413 and HRP-414 can be accessed by clicking the Library link in CATS IRB (<http://irb.psu.edu>).

3.1 Inclusion Criteria

List the criteria that define who will be included in your study.

- Healthy women between the ages of 18 and 45 years (Controls), taking oral contraceptive or with regular menses every 26-34 days
- Women between the ages of 18 and 45 years with endometriosis (diagnosis by prior laparoscopy by subject's own physician, and reported by the subject to the researchers)
- Tylenol if the subject has acute pain is allowed
- Contraceptive use is allowed

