3.2 Exclusion Criteria

List the criteria that define who will be excluded in your study.

- Use of nicotine-containing products (e.g. smoking, chewing tobacco, etc.)
- Diabetes (HbA1C .6.5%)
- BP>140/90
- Taking pharmacotherapy that could alter peripheral vascular control (e.g. insulin sensitizing, cardiovascular medications)
- Pregnancy
- Breastfeeding
- Taking illicit and/or recreational drugs
- Abnormal liver function
- Abnormal creatine phosphokinase (CPK)
- Rash, skin disease, disorders of pigmentation, known skin allergies
- Diagnosed or suspected metabolic or cardiovascular disease
- Persistent unexplained elevations of serum transaminases
- Known allergy to latex or investigative substances (including Lipitor)
- Previous adverse reaction to Lipitor or statin

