7.0 Study Design and Procedures

7.1 Study Design

Describe the type/design of trial to be conducted (e.g., double-blind, placebo controlled, parallel design, etc.). Provide a schematic diagram of study design, procedures and stages, if appropriate.

Two groups of women complete this study: 1) healthy women between the ages of 18 and 45 years (Controls); 2) women between the ages of 18 and 45 years with endometriosis. Each subject participates in a cutaneous microdialysis (MD) experiment before and after 6-9 days of oral atorvastatin (Lipitor) therapy (10mg/day). Each MD experiment includes a blood draw (e.g. miRNA, soluble LOX receptor, OxLDL, IL6, IL17, TNF α). The microdialysis experiments combine an acetylcholine dose response, perfusion of investigational agents, and local heating of the skin to explore the role of microRNA (miRNA) activation of LOX-1 receptor mechanisms in endothelial dysfunction associated with endometriosis.

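### Only controls are required to be healthy (undefined), so chronic inflammatory disease that the exclusions do not name can enter the endometriosis group more readily and bias the group contrast towards Aim 1

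*Combined protocol and SAP*

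**What the plan says.** The two groups enter through different wording in Section 3.1.

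- Controls: "Healthy women between the ages of 18 and 45 years (Controls), taking oral contraceptive or with regular menses every 26-34 days".
- Cases: "Women between the ages of 18 and 45 years with endometriosis (diagnosis by prior laparoscopy by subject's own physician, and reported by the subject".

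Section 7.1 draws the same distinction: "1) healthy women between the ages of 18 and 45 years (Controls); 2) women between the ages of 18 and 45 years with endometriosis". Neither section defines healthy.

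The exclusions in Section 3.2 apply to everyone. Those that bear on this point are "Diagnosed or suspected metabolic or cardiovascular disease", "Rash, skin disease, disorders of pigmentation, known skin allergies", abnormal liver function or CPK, diabetes, raised blood pressure, and "Taking pharmacotherapy that could alter peripheral vascular control (e.g. insulin sensitizing, cardiovascular medications" and the like. No autoimmune, joint, bowel or airway disease, nor chronic inflammatory disease in general, is named. Section 7.4.6.5 adds case-by-case exclusion, but of medications rather than diagnoses.

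On mechanism, Section 2.1 states: "LOX-1 is a ubiquitously expressed scavenger receptor, stimulated by oxLDL, Ang II, and other inflammatory cytokines". It adds that LOX-1 signalling ends in endothelial dysfunction. Section 2.3 makes chronic systemic inflammation acting through LOX-1 the premise of the study.

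**The concern.** Specific Aim 1 attributes any difference between the groups in LOX-1 activation and endothelial function to endometriosis. That attribution needs the groups to be alike in other causes of inflammation. The eligibility text does not secure this, because a general health requirement is placed on one group only.

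The possible contaminant is not a bystander. On the protocol's own account, another inflammatory disease would act on the pathway under test. It could raise soluble LOX-1 and the cytokines drawn at each experiment (IL6, IL17, TNF-alpha), and it could lower the skin blood flow response that forms the primary endpoint. If it is commoner among cases because of how they are admitted, the group contrast is pushed in the hypothesised direction. Hypotheses 2A and 2B, which relate microRNAs to LOX-1 and to endothelial function within cases, are exposed as well, since a few women with a second source of inflammation could drive the relation.

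**Working it through.** The documents give no comorbidity rate, group split, effect size or standard deviation that bears on this point, so there is no stated figure to reproduce. The check is one of eligibility logic.

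**Step 1. Apply the criteria to one woman.** Take a woman of 30 with chronic joint or bowel inflammation who takes no drug judged to be vasoactive.

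| Test | As a case | As a control |
|---|---|---|
| Age (3.1) | passes | passes |
| Health requirement (3.1, 7.1) | none stated | must be healthy; probably fails |
| Named disease exclusions (3.2) | passes | passes |
| Medication rules (3.2, 7.4.6.5) | passes | passes |
| Result | eligible | probably refused |

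The one line that separates the columns is the undefined word.

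**Step 2. Look for a later safeguard.**

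- Section 3.3.1 lets the team end participation when a subject's health adversely affects the study. This is a discretionary withdrawal rule, not an entry criterion.
- Section 8.3 promises potential confounders as covariates but names none. Section 8.1 plans 6 completers. With two groups, the between-subject residual degrees of freedom are 6 − 2 = 4, and each covariate costs one, so four covariates leave 4 − 4 = 0. If a condition occurred only in cases, there would also be no affected control from which to separate its effect from the group effect.

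**Step 3. Which comparisons are exposed.**

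- Control versus endometriosis (skin blood flow, soluble LOX-1, cytokines): exposed.
- MicroRNA relations within cases: exposed.
- Pre- versus post-statin and probe site versus probe site, as main effects: each woman is her own control, so a stable comorbidity does not confound them. An interaction of either with group is again a group comparison and would be exposed.

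**Step 4. Illustration on assumed inputs only.** Let p be the share of admitted cases with such a disease and n the number of cases. The chance of at least one affected case is 1 − (1 − p)^n. The 6 completers are not divided by group in the protocol, so n is taken as 3, with a range of 2 to 4.

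| Assumed p | n = 2 | n = 3 | n = 4 |
|---|---|---|---|
| 5% | 10% | 14% | 19% |
| 10% | 19% | 27% | 34% |
| 20% | 36% | 49% | 59% |

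For example, 1 − 0.95³ = 0.143. One affected case moves the case mean by 1/n of the disease's own effect: 1/2, 1/3 or 1/4. That effect is unknown, so the bias itself cannot be computed.

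**The case against.** The best reply is that healthy may be no more than a label for women without endometriosis, with the real health screen in Section 3.2, which is identical for both groups. The screening text (Section 7.2.1) supports this in part: it expects some participants to take thyroid medication, asks only for a TSH value, and does not confine this to cases. A reader might infer from Section 3.1 that inflammatory disease can occur in cases only and is absent from controls by rule. The documents do not support that, since an undefined word guarantees nothing about controls. What stands is that the written standard differs between the groups and probably works unequally.

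A reader might also infer that any chronic inflammatory disease is admissible in a case. That goes too far. Skin, liver, metabolic and cardiovascular disease are excluded in both groups, and the medication rules would remove some treated patients. The gap is limited to what remains.

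Thirdly, this is a pilot. Section 8.3 uses it to note variance for a power analysis, with the ANOVA only if appropriate, and Sections 2.3 and 8.1 expect later modification. That lowers the immediate stakes. It does not remove them, because the pilot's variance and its criteria feed the final protocol.

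Finally, the share that one woman contributes to the case mean reflects the small sample, not this criterion. That is correct.

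**Conclusion.** The concern holds in a limited form. As written, a woman with endometriosis and an autoimmune or chronic inflammatory disease outside the listed exclusions is eligible as a case, while the same disease would probably bar a control. The disease acts on the pathway that the protocol tests, so the control-versus-endometriosis contrast can be biased towards Aim 1, and the microRNA relations within cases can be distorted. Neither discretionary withdrawal nor unnamed covariates cures this.

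The conclusion rests on healthy carrying some meaning beyond the absence of endometriosis, and on the protocol's own statement that cytokines stimulate LOX-1. The size cannot be quantified from the documents. The percentages above are arithmetic on assumed inputs, not estimates, and should not be read as the probability that this trial is biased. Nor does the point reach the statin or probe-site main effects, so it would be wrong to infer that the whole study is confounded.

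**What to change.** Apply one health standard to both groups.

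1. In Section 3.1, and to match in 7.1, have the case criterion call for otherwise healthy women with endometriosis.
2. In Section 3.2, add for both groups: diagnosed autoimmune or other chronic inflammatory disease. The added exclusion also gives the word healthy some defined content.
3. Ascertain it from the health history already taken at screening (Section 7.2.1), so that no new procedure is needed.

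The cost is a wording amendment, the loss of a few cases, and a case group slightly less representative of women with endometriosis. If that loss is unacceptable, record such conditions in both groups and pre-specify a sensitivity analysis of the group contrast without those subjects. With 6 completers that analysis would be descriptive, but the rule would be in place for the larger study.

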3.2 Exclusion Criteria

List the criteria that define who will be excluded in your study.

- Use of nicotine-containing products (e.g. smoking, chewing tobacco, etc.)
- Diabetes (HbA1C .6.5%)
- BP>140/90
- Taking pharmacotherapy that could alter peripheral vascular control (e.g. insulin sensitizing, cardiovascular medications)
- Pregnancy
- Breastfeeding
- Taking illicit and/or recreational drugs
- Abnormal liver function
- Abnormal creatine phosphokinase (CPK)
- Rash, skin disease, disorders of pigmentation, known skin allergies
- Diagnosed or suspected metabolic or cardiovascular disease
- Persistent unexplained elevations of serum transaminases
- Known allergy to latex or investigative substances (including Lipitor)
- Previous adverse reaction to Lipitor or statin

3.3 Early Withdrawal of Subjects

3.3.1 Criteria for removal from study

Insert subject withdrawal criteria (e.g., safety reasons, failure of subject to adhere to protocol requirements, subject consent withdrawal, disease progression, etc.).

Participants may withdraw at any time. We may end the participant's role if we determine that her/his health or behavior adversely affects the study or increases the risks beyond those approved by the Institutional Review Board and agreed upon by the subject in the informed consent.

3.3.2 Follow-up for withdrawn subjects

Describe when and how to withdraw subjects from the investigational product or study; the type and timing of the data to be collected for withdrawal of subjects; whether and how subjects are to be replaced; the follow-up for subjects withdrawn from investigational treatment.

The study team will not contact subjects who voluntarily withdraw. The study team contacts subjects who withdraw due to an untoward or adverse event within 5 days of the withdrawal for follow-up and feedback.

4.0 Recruitment Methods

4.1 Identification of subjects

Describe the methods that will be used to identify potential subjects or the source of the subjects. If not recruiting subjects directly (e.g., database query for eligible records or samples) state what will be queried, how and by whom.

StudyFinder: If you intend to use StudyFinder (<http://studyfinder.psu.edu>) for recruitment purposes, please indicate this in section 4.1 along with any other methods for identifying subjects. Note that information provided in this protocol should be consistent with information provided on the StudyFinder page in your CATS IRB study.

For Penn State Hershey submissions using Enterprise Information Management (EIM) for recruitment, attach your EIM Design Specification form on the Basic Information page in CATS IRB (irb.psu.edu). See HRP-103 Investigator Manual, "What is appropriate for study recruitment?" for additional information.

We recruit subjects from Centre County, PA and surrounding regions utilizing CTSI resources at University Park. Also, we advertise for subjects (see below). Interested persons contact us. We also avail ourselves of lists of potential subjects maintained by the CRC and our lab. People on these lists have screened for other studies and indicated that they wished to be maintained on a list of potential subjects to be contacted in the event that they may qualify for additional studies. We will use StudyFinder.

4.2 Recruitment process

Describe how, where and when potential subjects will be recruited (e.g., approaching or providing information to potential subjects for participation in this research study).

We advertise for subjects. Interested persons contact us. We discuss the study's purpose and protocol as well as the qualifications for the study with the potential subject. We discuss the informed consent with them. We invite potential subjects to tour the lab, and ask questions.

4.3 Recruitment materials

List the materials that will be used to recruit subjects. Add recruitment documents to your study in CATS IRB (<http://irb.psu.edu>) on the "Consent Forms and Recruitment Materials" page. For advertisements, upload the final copy of printed advertisements. When advertisements are taped for broadcast, attach the final audio/video tape. You may submit the wording of the advertisement prior to taping to preclude re-taping because of inappropriate wording, provided the IRB reviews the final audio/video tape.

StudyFinder: If you intend to use StudyFinder (<http://studyfinder.psu.edu>) for recruitment purposes, you do not need to upload a separate recruitment document for information placed on the STUDYfinder site to your study in CATS IRB. Necessary information will be captured on the StudyFinder page in your CATS IRB study.

Study Finder
Newspaper/magazine ads
Letters/Emails to potential participants
Flyers/posters
Web Sites
Listserv
Script – Verbal (i.e., telephone, face-to-face, classroom)

Note: We advertise through various listservs on and off campus that target under-represented groups (e.g. FOBA) as well as listservs belonging groups (e.g. endometriosis support/info groups) and others as we become aware of them.

Note: We use the information from the uploaded ad and/or the phone script in other forms of recruitment (e.g. emails, listservs, websites).

